10.4.3 Electroencephalography

Electroencephalography (EEG) is performed at Visit 1 and appropriate data will only be listed by subject.

10.4.4 Computed tomography/ Magnetic resonance imaging

Computed tomography (CT) scan/ magnetic resonance imaging (MRI) is performed at Visit 1 and will be listed by subject and type of image.

10.4.5 Physical examination

A physical examination is performed at Visits 1, 3, and 7/EDV, Visit 8 and the Safety Visit and may also be performed at unscheduled visits, although findings are only recorded on the CRF at rization Visit 1. A listing of abnormal physical examination findings at Visit 1 will be provided; no summaries of physical examination findings are planned.

10.4.6 Neurological examination

A neurological examination is performed at Visits 1, 3, and 7/EDV, Visit 8 and at the Safety Visit and may also be performed at unscheduled visits. A listing of neurological examination results will be provided; no summaries of neurological examination findings are planned.

10.4.7 **Psychiatric and mental status**

An evaluation of Psychiatric and Mental Status is performed at Visits 1, 3, and 7/EDV, Visit 8 and at the Safety Visit and may also be performed at unscheduled visits. A listing of Psychiatric and Mental Status results will be provided; no summaries of Psychiatric and Mental Status findings are planned.

Columbia-Suicide Severity Rating Scale 10.4.8

With global amendment 1 to the protocol, the Columbia-Suicide Severity Rating Scale (C-SSRS) has been added as an assessment at all study visits to assess suicidality. Specific rules are this documentication provided to the study sites with regard to the identification of AEs or SAEs based on the outcome of this assessment. Because clinical events of interest will be recorded as AEs or SAEs, no study variable is defined for this assessment and no analyses are planned for the C-SSRS within the context of this study. However, subject data listings of the data for the C-SSRS will be

Confidential

ris document cannot be used to support any nations the book of the loss of the book of the

12 **APPENDICES**

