# 2.4 Safety with BRV

In the BRV clinical development program, 3970 subjects have been exposed to BRV (unique exposures) as of 14 Jan 2019.

In Phase 2/3 studies, a favorable safety and tolerability profile has been demonstrated for BRV. The discontinuation rate and the discontinuation rate due to treatment-emergent adverse events (TEAEs) were low and similar to PBO for all studies. The most common adverse drug reactions in subjects with partial seizures were somnolence, sedation, dizziness, fatigue, and nausea/vomiting. The overall incidence of serious adverse events (SAEs) was low and similar to PBO. There were no clinically relevant changes in laboratory values, vital signs or ECG abnormalities.

In addition, the safety of BRV as long-term adjunctive treatment has been evaluated in 5 LTFU studies (N01125, N01379, N01199, N01315, and N01372). The safety profile in the open-label extension studies (up to 8 years) was consistent to that observed in the short-term, PBO-controlled studies.

For additional details on safety and efficacy of BRV, please refer to the Investigator's Brochure (IB).

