### **Psychiatric and mental status** 11.3.5

Psychiatric and mental status will be reported by recording the presence or absence of psychiatric symptoms, mental impairment, and behavioral problems at time points specified in the schedule of study assessments (Table 5–1). Clinically significant new or worsened abnormalities will have to be reported as AEs.

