### Assessment of suicidality 11.3.8

Suicidality will be assessed by trained study personnel using the C-SSRS. This scale will be used for Baseline/Selection as well as to assess suicidal ideation and behavior that may occur during the study. The C-SSRS will be completed at time points specified in the schedule of study assessments (Table 5-1).

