- Dose Normalized Plasma Level (µg/mL/50mg): equivalent to 50mg/day

SAFETY ANALYSES 10

orization Safety is assessed with AEs, laboratory tests (blood chemistry, hematology, urinalysis, and pregnancy test), vital signs, body weight, ECGs, physical examination, neurological (examination, mental status, and psychiatric status. Summary tables will be provided for AEs; blood chemistry, hematology, and urinalysis; vital signs; body weight; and ECGs. No summary tables will be provided for pregnancy testing, physical examination, neurological examination, mental status, or psychiatric status.

All safety summaries will be based on the SS.

Regarding safety for the Open-Label Temporary Period, it will be summarized separately from other preceding study periods as described in Section 3.2.2.

10.1 **Extent of exposure**

The duration of study medication exposure for the Treatment Period will be calculated as the date of last dose of IMP during the Treatment Period minus the date of first dose of IMP plus 1 day. The overall duration of study medication exposure for the entire study will be calculated as the date of last dose of IMP minus the date of first dose of IMP plus 1 day.

The duration of study medication exposure and the overall duration of IMP exposure will be summarized with quantitative descriptive statistics for the Treatment Period and for the entire study (except the Open-Label Temporary Period), respectively, for the SS. The number and percentage of subjects with the following categories of durations of study medication exposure for the Treatment Period and the entire study will also be summarized:>0 weeks, >=2 weeks, >=4 weeks, >=6 weeks, >=8 weeks, >=10 weeks, and >=12 weeks.

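### Mental and psychiatric status (declared safety variables) and the C-SSRS get listings only, so findings that do not become adverse events enter no by-arm summary

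*SAP*

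**What the plan says.** **Mental and psychiatric status.** Protocol 4.3.2 and SAP 2.2.4 both list these among the other safety variables. Protocol 11.3.5 has the sites record the presence or absence of psychiatric "symptoms, mental impairment, and behavioral problems at time points specified in the schedule" of assessments, and requires an AE for any new or worsened abnormality that is clinically significant. SAP 10 opens by naming both among the measures with which safety is assessed. It then states that no summary "tables will be provided for pregnancy testing, physical examination, neurological examination, mental status, or psychiatric status". SAP 10.4.7 confirms this: "A listing of Psychiatric and Mental Status results will be provided; no summaries of Psychiatric and Mental Status findings are planned".

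**C-SSRS.** Protocol 11.3.8 uses the scale for selection and also "to assess suicidal ideation and behavior that may occur during the study". SAP 10.4.8 says that it "has been added as an assessment at all study visits to assess suicidality", but that no study "variable is defined for this assessment and no analyses are planned for the C-SSRS within the" context of this trial; subject listings are provided. The SAP gives its reason: sites hold specific rules for identifying AEs and SAEs from the scale, so clinical events of interest will reach the AE data.

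**AE tables.** SAP 10.2.1 summarizes TEAEs by SOC and PT, including treatment-emergent SAEs and TEAEs leading to discontinuation of drug or study. Under SAP 3.1, safety summaries are shown for each treatment group and for both BRV groups combined.

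**The concern.** A declared safety variable with a pre-dose value, on-treatment values and a concurrent placebo arm would normally be summarized by arm. Here two such variables are ruled out of every summary table, and their only route to a by-arm result passes through a judgment of clinical significance. The C-SSRS has a similar gap: its route to a by-arm result is a set of conversion rules that the protocol and SAP cite but do not contain. Findings that stop short of an AE can be read subject by subject in a listing but are not set against placebo in any planned output.

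**Working it through.** The plan states no figure on this point and no arithmetic applies. The check sets the relevant sections side by side.

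**Step 1: how comparable measures are handled** (Protocol 4.3.2 and Table 5-1; SAP 2.2.4 and 10.4.1 to 10.4.8).

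| Measure | Declared variable | Collected after first dose | Planned output |
|---|---|---|---|
| ECG | Yes | Visits 4, 5, 7/EDV, 8 | By-arm counts, with a separate category for abnormalities lacking clinical significance; normal/abnormal shifts |
| Vital signs, weight | Yes | Visits 4 to 7, EDV, 8, Safety Visit | By-arm values, changes and PCST counts |
| Mental and psychiatric status | Yes | Visit 7/EDV, 8, Safety Visit | Listing only |
| Neurological examination | Yes | Visit 7/EDV, 8, Safety Visit | Listing only |
| Physical examination | Yes | Visit 7/EDV, 8, Safety Visit, but CRF findings at Visit 1 only | Listing of Visit 1 abnormalities |
| C-SSRS | No | Every visit | Listing only |

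For ECG and vital signs, abnormal values are tabulated by arm whether or not they become AEs. For physical examination the SAP gives a practical reason for having no summary: post-baseline findings are not on the CRF. It states no such limit for mental and psychiatric status.

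**Step 2: is a shift table feasible?** Psychiatric and mental status is assessed at Visits 1 and 3. Protocol section 7 puts the first intake of newly dispensed medication in the evening of the visit, and SAP 3.9.6 says only the evening dose is taken on the first day. Visit 3 is therefore pre-dose. SAP 3.3 already defines Baseline as the last non-missing value before first dose. Visit 7/EDV supplies the on-treatment value.

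**Step 3: what reaches a by-arm table now?**
- A clinically significant new or worsened psychiatric or mental abnormality becomes an AE (Protocol 11.3.5) and is tabulated by arm (SAP 10.2.1, 3.1).
- A C-SSRS outcome that the site rules identify as an AE or SAE is tabulated in the same way.

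**Step 4: what does not?**
- New or worsened psychiatric symptoms, mental impairment or behavioral problems judged not clinically significant.
- Positive C-SSRS answers that the site rules do not turn into AEs. Protocol 11.1 contains no conversion rule, and the site rules are not in either document, so the size of this group cannot be determined.

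**The case against.** The case for the plan is substantial. SAP 10.4.8 states its choice and justifies it. The C-SSRS appears in neither list of safety variables. Protocol 13.4.1 describes AE summaries only, so the SAP breaks no commitment made there. Clinically significant changes must be reported as AEs and are compared with placebo in several TEAE tables. The subject listings would allow a count by hand. Exclusion criterion 29 removes subjects with a lifetime suicide attempt or recent ideation at Question 4 or 5, so a C-SSRS table may be nearly empty.

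Most of this stands, and it rules out three stronger readings that a reader might infer:

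- *That suicidality and behavioral effects are never compared between arms.* They are, descriptively, once recorded as TEAEs. Nor does tabulation by PT leave them wholly scattered, because the tables also have an SOC level.
- *That conversion of C-SSRS answers into AEs is incomplete.* The SAP says that rules exist. Not being able to see them is no evidence that they fail.
- *That the known safety profile points to a psychiatric signal.* Protocol 2.4 says "The most common adverse drug reactions in subjects with partial seizures were somnolence, sedation, dizziness", followed by fatigue and nausea/vomiting. None of these is a suicidality or psychiatric term.

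What the objection does not answer is the handling of the declared variables. A listing is not a by-arm summary, the AE route stops at clinical significance, and the SAP does not apply that limit to ECG findings.

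**Conclusion.** The point holds as a minor reporting gap. It is firmest for mental and psychiatric status: both are declared, SAP 10 names them among the measures of safety, and both are then excluded from every summary by an explicit rule. It is weaker for the C-SSRS, which is undeclared and has a stated AE route. There the case is only that a scale collected at every visit to detect suicidality on study could be reported against placebo at little cost.

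The loss is limited to the two groups in Step 4, and its size cannot be estimated from the documents. Sample size, type I error and the efficacy analyses are untouched. The conclusion assumes that the CRF holds the presence/absence items of Protocol 11.3.5 in tabulable form at each scheduled visit, and that no by-arm summary is planned in a document outside the protocol and SAP.

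**What to change.** 1. **SAP 10 and 10.4.7.** Replace the statements that no summaries are planned with a shift table by treatment group on the Safety Set. Show absent/present from the last pre-dose assessment to Visit 7/EDV, separately for psychiatric symptoms, mental impairment and behavioral problems, with Visit 8 and the Safety Visit also shown.
2. **SAP 10.4.8.** Add one descriptive table by treatment group, on the Safety Set, of subjects with any treatment-emergent positive C-SSRS ideation or behavior response. Define treatment-emergent there and take the response categories from the CRF, because the protocol and SAP describe only Questions 4 and 5.
3. **Optional, SAP 10.4.6.** Do the same for the neurological examination, which is also declared and only listed.

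No hypothesis test is needed, and no referral, withdrawal or AE-reporting rule changes. The cost is SAP wording and a few extra tables from data already collected and listed, probably with sparse counts that should be read descriptively.

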12.1 Actual BRV dose conversion table

Table 12.1: Conversion from blinded daily dose to unblinded BRV daily dose

| UCB Statistical Analysis P | lan Bi | rivarace | tam | | | | | | | jj | xx A | ug 2022 EP0083 |
|-------------------------------|--|----------|--------|-------------|--------|--------|-----|-----|------|-----|------|-------------------|
| | PPENDICES | | | | | | | | nori | | | |
| | ctual BRV dose conversion table onversion from blinded daily dose to ur | nblind | led BF | RV da | ily do | se | ~0 | 30 | 0 | | | |
| | | | Blin | ded No | ominal | Dose (| | | | | | |
| Treatment group | Period or Visit | 0 | 25 | 50 | 75 | 100 | 125 | 150 | 175 | 200 | 225 | 250 |
| 200mg/day | Start day of Treatment Period | 0 | 0 | 50 | 50 | 100 | 100 | | | | | |
| | Treatment Period (except first and last dates) | 0 | 0 | 50 | 50 | 100 | 100 | 150 | 150 | 200 | 200 | 200 |
| | Day of end Treatment and start Transition | 0 | 25 | 50 | 75 | 100 | 125 | 150 | 175 | 175 | | |
| | Transition Period (except first and last dates) | 0 | 25 | 50 | 75 | 100 | 125 | 150 | | | | |
| | Last day of Transition Period | 0 | 25 | 50 C | 75 | | | | | | | |
| 50mg/day | Start day of Treatment Period | 0 | 25 | 0 | 25 | 0 | 25 | | | | | |
| | Treatment Period (except first and last dates) | 0 | 25 | 50 | 25 | 50 | 25 | 50 | 25 | 50 | 25 | 50 |
| | Day of end Treatment and start Transition | 0 | 25 | 50 | 25 | 50 | 25 | 50 | 25 | 50 | | |
| | Transition Period | -0 | 25 | 50 | 25 | 50 | 25 | 50 | | | | |
| | Last day of Transition Period | 0 | 25 | 0 | 25 | | | | | | | |
| РВО | Start day of Treatment Period | 0 | 0 | 0 | 0 | 0 | 0 | | | | | |
| | Treatment Period (except first and last dates) | 0 | 0 | 0 | 0 | 0 | 0 | 0 | 0 | 0 | 0 | 0 |
| | Day of end Treatment and start Transition | 0 | 0 | 0 | 0 | 0 | 0 | 0 | 0 | 0 | | |
| | Transition Period (except first and last dates) | 0 | 0 | 0 | 0 | 0 | 0 | 0 | | | | |
| | Last day of Transition Period | 0 | 0 | 0 | 0 | | | | | | | |

his locul app Note: Figures in italics indicate that there are two theoretically possible doses, of which the higher one is selected.

Confidential

12.2 **PCST** criteria

12.2.1 Laboratory assessments - PCST

Hematology 12.2.1.1

| The following criteria will b values. | be applied in the | determination of Po | CST laboratory assessment |
|--|-------------------|---------------------|---------------------------------------|
| 12.2.1.1 Hematolog | У | | Alle |
| Table 12–2: Hematolog | y PCST criteri | a | dille |
| PARAMETER | AGE RANGE | UNIT (standard) | ABNORMALITY CRITERIA (standard) |
| Hematocrit | <2y | % | ≤27, >45 |
| | 2y - <18y | | ≤ 29, >47 |
| | ≥18y | | ≤85% of LLN, ≥115% of ULN |
| Hemoglobin | <2y | g/L | ≤ 90, ≥ 150 |
| | 2y - <18y | 1 | ≤95,>160 |
| | ≥18y | | \leq 85% of LLN, \geq 115% of ULN |
| WBC/Leukocytes | <12y | G/LO | <3.5,>15.0 |
| | ≥12y | | <3.0, >12.0 |
| Neutrophils Absolute | >1m | G/L | <1.5 |
| Lymphocytes | <6m | % | ≤30.0 |
| | 6m - <6y | e de | ≤22.0 |
| | 6y - <18y | T.C. | ≤12.0, ≥80.0 |
| | ≥18y | e' | ≤10.0, ≥80.0 |
| Basophils | >lm | % | ≥3.0 |
| Eosinophils | >1m | % | ≥10.0 |
| Monocytes | >1m | % | ≥20.0 |
| Platelets | >1m | G/L | ≤100, >600 |
| RBC/ Erythrocytes | <2y | T/L | <3.0 |
| | ≥2y | | <3.5 |

Abbreviations: F=female; M=male; m=month; y= year. A month is defined as 30 days; a year is defined as 365.25 days.

Blood chemistry 12.2.1.2

Table 12–3: Chemistry PCST criteria

| PARAMETER | AGE RANGE | UNIT (standard) | ABNORMALITY CRITERIA (standard) |
|------------|-----------|--------------------|------------------------------------|
| AST (SGOT) | <14y | U/L | >180 |

| PARAMETER | AGE RANGE | UNIT | ABNORMALITY CRITERIA |
|------------------------|------------|------------|----------------------|
| | | (standard) | (standard) |
| | ≥14y | | >144 |
| ALT (SGPT) | 1y - <18y | U/L | >90 |
| | ≥18y | | >123 |
| Alkaline Phosphatase | <4y | U/L | >690 |
| | 4y - <10y | - | >834 |
| | 10y - <18y | | >1174 |
| | ≥18y | | >432 (F), >933 (M) |
| GGT | <6m | U/L | >522 |
| | 6m - <1y | | >279 |
| | 1y - <13y | | >66 |
| | 13y - <18y | 1 | >126 |
| | ≥18y | OT O | >255 |
| Total Bilirubin | >1m | umol/L | ≥25.656 |
| Total Protein | 2m-<1y | g/L | <30,>100 |
| | ≥1y | N NR S | <43,>100 |
| Albumin | <1y | g/L | <16,>60 |
| | ≥1y | to asi | <24,>70 |
| BUN | <1y | mmol/L | >7.497 |
| | ≥1y | 0' | >10.71 |
| Urea | <1y | mmol/L | >7.014 |
| | ≥1y | | >10.02 |
| Creatinine | 1y - <10y | umol/L | >79.56 |
| CO. | 10y - <16y | | >123.76 |
| | ≥16y | | >141.44 |
| Creatinine Clearance * | All | mL/s | <1.169 |
| Calcium | <1y | mmol/L | <1.725, >3.05 |
| YOU SKI | 1y - <18y | 1 | <1.85, >2.925 |
| U. | ≥18y | 1 | ≤1.975, ≥2.775 |
| Phosphorous | <1y | mmol/L | <0.5814, >2.6486 |
| | ≥1y | 1 | <0.5814, >2.3902 |
| Potassium | <1y | mmol/L | <3.0, >6.5 |

| PARAMETER | AGE RANGE | UNIT (standard) | ABNORMALITY CRITERIA (standard) |
|-------------------|------------|--------------------|------------------------------------|
| | ≥1y | | <3.0, >5.8 |
| Sodium | >1m | mmol/L | ≤130,≥150 |
| Glucose | >1m | mmol/L | <2.775, >9.99 |
| Total Cholesterol | 1y - <18y | mmol/L | >6.475 |
| | ≥18y | | >7.77 |
| LDL (calculated) | 1y - <18y | mmol/L | >3.626 |
| | ≥18y | | >5.18 |
| HDL | ≤2y | mmol/L | <0.259 |
| | >2y | | <0.518 |
| Triglycerides | <1y | mmol/L | >8.475 |
| | ≥1y | 1 | >2.825 |
| Uric Acid | <1y | umol/L | >457.996 |
| | 1y - <13y | | >386.62 |
| | 13y - <18y | | >511.528 |
| | ≥18y | | >404.464 (F), >571.008 (M) |
| Thyroxine (T4) | <1y | nmol/L | ≤55.3453,≥236.8264 |
| | ≥ly | | ≤48.9098,≥173.7585 |
| Globulin | <1y | g/L | <10,>38 |
| | ≥1y | 0' | <12,>44 |

Abbreviations: ALT= alanine aminotransferase: AST = aspartate aminotransferase; BUN = blood urea nitrogen; dL = deciliter; F=female; GGT: gamma-glutamyltransferase; HDL = high density lipoprotein; LDL = low density lipoprotein; L = liter; M=male; m = month (a month is defined as 30 days) mg = milligram; mmol = millimoles; μg = microgram; U = unit; ULN = upper limit of normal; y = years (a year is defined as 365.25 days) * Schwartz equation (patients <12): Cr Cl ml/min = [Height (cm) * 0.55] / serum creatinine; Cockroft equation

(patients >12): Male: Cr Cl ml/min = [(140-age) × body weight (kg)] / (72 × serum creatinine); Female: Cr Cl ml/min = [(140-age) × body weight (kg)] / (72 × serum creatinine)] × 0.85

12.2.1.3 Urinalysis

[Instruction]

Qualitative urine parameters are generally reported by a descriptive score, which differs among laboratories. For data analysis purpose, a 4-point scale is used. Five-point, 6-point, or 7-point scales will be collapsed into a 4-point scale first. A value is considered possibly clinically significant treatment-emergent abnormal if an upward shift of at least 2 degrees from the baseline occurs under investigational treatment. To collapse the results in a 5-point scale into a 4point scale, the lowest 2 positive results will be combined (see example below). For results reported with a scale of more than 5-point, please consult your study physician for how to collapse into 4-point scale.

| Original 5-point Scale | 4-point Scale | | |
|------------------------|----------------------------------|---------------------|---|
| Negative/None | Negative/None | | 6 |
| Trace/Rare/Mild/A Few | Trace/1+/Rare/Mild/A Few | | |
| 1+ | | | |
| 2+/Mod | 2+/Mod | .×C ⁰ `. | |
| 3+/Sev | 3+/Sev | n s. | |
| [Application] | | | |
| Table 12–4: Urinalysis | 4-point scales for PCST criteria | CIT KON | |

Table 12–4: Urinalysis 4-point scales for PCST criteria

| PARAMETER | Original Scale | 4-point Scale for PCST |
|------------------------------|--|--|
| Protein | Negative, Trace, 30mg/dL, 100mg/dL, ≥300mg/dL, ≥1000mg/dL | Negative, (Trace, 30mg/dL), 100mg/dL, (≥300mg/dL, ≥1000mg/dL) |
| Glucose | Negative, 100mg/dL, 250mg/dL, 500mg/dL, ≥1000mg/dL | Negative, (100mg/dL, 250mg/dL), 500mg/dL, ≥1000mg/dL |
| Ketones | Negative, Trace, 15mg/dL, 40mg/dL, ≥80mg/dL, ≥160mg/dL | Negative, (Trace, 15mg/dL), 40mg/dL, (≥80mg/dL, ≥160mg/dL) |
| Hemoglobin (Occult blood) | Negative, Trace, Small, Moderate, Large | Negative, (Trace, Small), Moderate, Large |
| Leukocyte Esterase | Negative, Trace, Small, Moderate, Large | Negative, (Trace, Small), Moderate, Large |

12.2.2 Vital sign assessments - abnormal

Abnormality criteria to be applied in the assessment of vital signs parameter values are given below.

Table 12-5: Vital sign PCST criteria

| [| PARAMETER | AGE RANGE | ABNORMALITY CRITERIA |
|---|------------------------------|------------|--|
| | Pulse Rate (beats/minute) | <6m | <100,>180 |
| | ×0° %. | 6m - <3y | <90, >150 |
| | 5 | 3y - <12y | <60,>130 |
| | | 12y - <17y | <50,>120 |
| | | ≥17y | <50 and a decrease from Baseline of \geq 15, >120 and an increase from Baseline of \geq 15 |

| PARAMETER | AGE RANGE | ABNORMALITY CRITERIA |
|--------------------------------------|------------|---|
| Systolic Blood Pressure (mmHg) | <6m | <60,>100 |
| | 6m - <3y | <70,>120 |
| | 3y - <12y | <80,>140 |
| | 12y - <17y | <90, >160 |
| | ≥17y | \leq 90 and a decrease from Baseline of \geq 20, \geq 180 and an increase from Baseline of \geq 20 |
| Diastolic Blood Pressure (mmHg) | <6m | <40,>65 |
| | 6m - <3y | <45,>75 |
| | 3y - <12y | <50, >80 |
| | 12y - <17y | <50, >105 |
| | ≥17y | <50 and a decrease from Baseline of \geq 15, \geq 105 and an increase from Baseline of \geq 15 |
| Respiratory Rate (breaths/minute) | <6m | <25, >55 |
| | 6m - <3y | <20, >45 |
| | 3y - <12y | <15 >35 |
| | ≥12y | <10,>25 |
| Temperature | >1m | >101°F (38.3°C) |
| Body Weight | 1m - <17y | <3% or 97% of the normal body weight growth curve ranges based on gender and the age of subject on date of weight assessment ^a |
| | ≥17y | \geq 10% change from Baseline (an increase or a decrease) ^a |

Abbreviations: m = month, y = year. A month is defined as 30 days; a year is defined as 365.25 days. ^a source: http://www.cdc.gow/growthcharts/: Once the subject reaches 17 years of age use the body curve criteria of a 17-year-old regardless of their age in the study.

The following table is used to judge PCST regarding body weight.

Body weight (kg) at the 3 and 97 percentiles of the distribution at each age in Japanese children

| | Ag (years-m | | 16-0 | 16-1 | 16-2 | 16-3 | 16-4 | 16-5 | 16-6 | 16-7 | 16-8 | 16-9 | 16-10 | 16-11 | 17-0 |
|---------------------|----------------|-----|-------|-------|-------|-------|-------|-------|-------|-------|-------|-------|-------|-------|-------|
| | Male | 3% | 45.66 | 45.89 | 46.11 | 46.33 | 46.53 | 46.73 | 46.93 | 47.11 | 47.29 | 47.47 | 47.64 | 47.80 | 47.97 |
| ·S | | 97% | 83.83 | 84.08 | 84.32 | 84.57 | 84.82 | 85.07 | 85.31 | 85.56 | 85.79 | 86.02 | 86.24 | 86.45 | 86.64 |
| $\langle c \rangle$ | Female | 3% | 41.04 | 41.11 | 41.18 | 41.25 | 41.31 | 41.37 | 41.43 | 41.49 | 41.55 | 41.60 | 41.66 | 41.71 | 41.76 |
| * | | 97% | 69.91 | 69.98 | 70.05 | 70.12 | 70.19 | 70.25 | 70.31 | 70.36 | 70.41 | 70.46 | 70.51 | 70.55 | 70.59 |

The dourgent cannot be used to support any name to the tool.

AMENDMENT TO THE STATISTICAL ANALYSIS PLAN 13 (SAP)

13.1 Amendment 1

- n sions or variat

- To update the company name from SPRL to SRL

Modifications and changes

Global changes

There are no global changes to the SAP during this amendment.

Specific changes

Change #1

INTRODUCTION (last sentence) 1

... The SAP is based on the following study document: Protocol Amendment 3.0 and 3.1 (01 Feb 2019).

Has been changed to:

The SAP is based on the following study document: Protocol Amendment 4 (10 Jan 020)

Change #2

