10.4 Vital signs, physical findings, and other observations related to safety

10.4.1 Vital signs

Systolic blood pressure (SBP), diastolic blood pressure (DBP), and pulse rate are assessed for Visits 1 through 7, EDV, Visit 8, and the Safety Visit and may also be assessed at unscheduled visits. Body weight is assessed at all of the same time points except for Visit 2.

Observed values for SBP, DBP, and pulse rate will be summarized for Visits 1 through 7, End of Treatment, Visit 8, and the Safety Visit. Changes from Baseline for SBP, DBP, and pulse rate will be summarized for Visits 4 through 7, End of Treatment, the Visit 8, and the Safety Visit. Same summaries will be provided for body weight.

The number and percentage of subjects with at least one PCST low values, and subjects with at least one PCST high value will be summarized for SBP, DBP, pulse rate, and body weight. Percentages will be relative to the number of subjects with an assessment within each study period. PCST criteria are defined in Section 12.2.2.

Vital signs measurements (absolute values and changes from Baseline) will be listed by visit and timing relative to dosing including changes from Baseline.

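### In SAP Table 12-5, footnote a contradicts the body-weight criterion for age 17 and over to which it is attached

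*SAP*

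**What the plan says.** SAP Section 12.2.2, Table 12-5, gives two body-weight rows:

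- **Under 17:** weight outside the 3rd or 97th percentile "of the normal body weight growth curve ranges based on gender and the age of subject on date of weight assessment".
- **17 and over:** at least "10% change from Baseline (an increase or a decrease").

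Both rows carry footnote a. The footnote cites a growth-chart web address as its source and then adds: "Once the subject reaches 17 years of age use the body curve criteria of a 17-year-old regardless of their age in the study".

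Below the table the SAP says "The following table is used to judge PCST regarding body weight" and prints limits headed "Body weight (kg) at the 3 and 97 percentiles of the distribution at each age in Japanese children". The columns run monthly from 16 years 0 months to 17 years 0 months.

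SAP Section 10.4.1 uses these criteria. It plans the number and percentage of subjects with at least one PCST low value, and with "at least one PCST high value will be summarized for SBP, DBP, pulse rate, and body weight". For definitions it refers only to Section 12.2.2.

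**The concern.** A programmer working from Section 12.2.2 meets two rules for the same adult subjects. One compares each weight with the subject's own Baseline. The other compares it with fixed limits for a 17-year-old, whatever the subject's age. Protocol Section 6 admits ages 16 to 80 (inclusion criterion 3), so nearly all of the permitted age range falls under the disputed row.

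If the footnote were coded, the PCST weight table would describe how heavy subjects are and not what happened to their weight on treatment. The SAP abbreviation list expands PCST with the words treatment-emergent, and Section 2.2.4 names the safety variable as change in body weight. A size-only count answers neither. If the rule is not settled in the plan, it will be settled in the code.

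A smaller inconsistency affects 16-year-olds. The footnote points to one growth-chart source, while the limits printed below come from Japanese children. SAP Section 2.3.3 lists Japan, Taiwan, China Mainland, the Philippines, Thailand, Singapore and Malaysia.

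**Working it through.** The plan states no figure to reproduce here. The check applies both printed rules to the same subjects.

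**Inputs**

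- Row rule (Table 12-5, age 17 and over): flag if |W − B| / B ≥ 10%, where B is Baseline weight and W the later weight.
- Footnote rule, using the 17-years-0-months column of the printed table: flag low if W is below the 3rd percentile, and high if above the 97th. The limits are 47.97 and 86.64 kg for men, and 41.76 and 70.59 kg for women.
- Entry weight (Protocol Section 6, inclusion criterion 4): 40 kg or more. No maximum is stated.

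**Step 1. Example adults under each rule**

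| Subject | Baseline to later weight | Change | Row rule | Footnote rule |
|---|---|---|---|---|
| Man | 47 to 47 kg | 0% | not flagged | low |
| Man | 90 to 90 kg | 0% | not flagged | high |
| Woman | 41 to 41 kg | 0% | not flagged | low |
| Woman | 75 to 75 kg | 0% | not flagged | high |
| Man | 75 to 67 kg | −8/75 = −10.7% | flagged | not flagged |
| Woman | 55 to 61 kg | +6/55 = +10.9% | flagged | not flagged |
| Man | 75 to 75 kg | 0% | not flagged | not flagged |

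The rules disagree in both directions. All these Baseline weights meet the weight criterion for entry.

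**Step 2. Largest loss the footnote rule could miss**

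- A man moving from the upper to the lower limit loses (86.64 − 47.97) / 86.64 = 38.67 / 86.64 = 44.6% without a flag.
- A woman doing the same loses (70.59 − 41.76) / 70.59 = 28.83 / 70.59 = 40.8%.

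These are arithmetic bounds, not expected cases.

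**Step 3. How many unchanged adults the footnote rule might flag**

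The documents give no weight distribution, so this step rests on assumption. Take weight as normal with distribution function F, truncated at the 40 kg entry limit:

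share flagged = [F(lower limit) − F(40) + 1 − F(upper limit)] / [1 − F(40)]

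- Example, men with mean 65 kg and SD 12 kg: about 6.0% low and 3.6% high, 9.7% in all after rounding.
- Men, means 60 to 75 kg and SDs 10 to 14 kg: 5.4% to 22.5%.
- Women, means 50 to 65 kg and SDs 8 to 12 kg: 4.4% to 33.5%.

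Under the row rule the share is 0% by definition.

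**Step 4. Does anything else in the SAP settle it?**

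Section 10.4.1 sends the reader back to Section 12.2.2, and no order of precedence between row and footnote is given. No screen for weights already outside the limits at Baseline is stated. By contrast, the urinalysis rule in Section 12.2.1.3 requires a shift from baseline.

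**The case against.** The strongest reply is that the intent is visible. Table 12-5 is organised by age, and the row for 17 and over states a complete criterion of its own. The adult rows for pulse, systolic and diastolic pressure also require a change from Baseline. The printed weight limits are for children and stop at 17 years 0 months, so they plainly serve the under-17 row. Flagging an adult of unchanged weight means letting a footnote override an explicit row and applying a children's table up to age 80.

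This stands as evidence of intent but does not remove the contradiction. The footnote mark is on the adult row, and its sentence applies from age 17 onwards. The statement that the printed table is used to judge body weight carries no age limit. The table's last column, 17 years 0 months, lies outside the under-17 row. A narrower reading, that the footnote covers only subjects who turn 17 on study, still fails: those subjects then fall under the 10% row too.

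Four stronger inferences are tempting, and the documents do not support them:

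- **Weight imbalances would look like drug effects.** Allocation is randomized 1:1:1, and no test is planned on this table. Section 10.4.1 also summarizes weight and its change from Baseline directly, which would help reveal a Baseline imbalance. Inflated counts and chance differences are possible; a systematic bias between arms is not shown.
- **The weight-change safety variable is compromised.** Those direct summaries do not use the PCST criteria.
- **The reference curve is undecided, or the Japanese limits are prescribed for every subject.** The SAP identifies the printed table as the one used, so what remains is an unreconciled citation. It sets no restriction by country, but it does not say the table applies to all. The documents give no count of 16-year-olds outside Japan.
- **The growth-curve criterion should go.** Once the footnote is corrected, the under-17 criterion conflicts with nothing, and it follows the same split at 17 as the other vital signs. Removing it would be a preference.

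**Conclusion.** The contradiction is real and sits in the current SAP text: the row and its own footnote give different body-weight criteria from age 17. The adult cut-offs and the disagreement in both directions follow directly from the printed figures.

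False flags arise only if the footnote is programmed for subjects aged 17 and over and values already outside the limits at Baseline are not screened out. The shares in the working depend further on assumed weight distributions and are for scale only.

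This is minor. It touches the descriptive PCST body-weight counts in Section 10.4.1 and nothing else. It merits correction because the footnote states a wrong rule outright, not because detail is missing.

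**What to change.** 1. In Table 12-5, delete the footnote sentence about the 17-year-old curve, or remove the footnote mark from the body-weight row for age 17 and over. The change-from-Baseline criterion then governs alone from age 17.
2. For 16-year-olds, name one reference curve by reconciling the cited growth-chart source with the printed Japanese table. If the printed table is the one intended, give its source and say whether it is used for subjects outside Japan.
3. Keep the under-17 criterion as it is.

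The cost is a few words in an SAP appendix and a check that the PCST weight program matches. No data collection or other planned analysis changes.
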